----------	--------------------------	----

TRIAL SUMMARY

Trial Title	Randomised controlled trial of the clinical and cost-effectiveness of cervical spine immobilisation following blunt trauma (SIS trial)	
Internal ref. number (or short title)	SIS trial	
Trial Design	A multi-centre, open-label, pragmatic, pre-hospital, non-inferiority randomised controlled trial with health economic evaluation to determine the effectiveness of immobilisation regimes involving movement minimisation and triple immobilisation (current NHS practice) in patients with cervical spine (c-spine) injury recruited in a pre-hospital setting.	
Trial Participants	Patients (any age) in a pre-hospital setting with potential or suspected c-spine injury.	
Planned sample size	8,316 participants	
Treatment Duration	The interventions will be administered at initial pre-hospital clinical assessment and will remain in place for as long as is clinically required.	
Follow-up Duration	Participants will be followed-up for 180 days	
Planned Trial Period	01 November 2022 – September 2025 with an internal pilot phase 01 November 2022 – 30 April 2023	
	Objectives	Outcome Measures
Primary	To determine whether movement minimisation is deemed non-inferior compared to triple immobilisation in relation to functional outcome at hospital discharge.	Functional Independence Measure (Motor) score
Secondary	To determine the effects of immobilisation techniques on clinical, patient-centred and economic outcomes pre-hospital, in hospital and at 180 days post-randomisation.	Need for pre-hospital analgesia Neurological change (randomisation to hospital discharge) Mortality (30, 90 and 180 days) Length of stay in critical care and hospital Further intervention for c-spine injury Costs and resource utilisation Adverse events
Quality of Life	To determine the effects of immobilisation techniques on patient-centred outcomes pre-hospital, in hospital and at 180 days post-randomisation.	Quality of life measurements (EQ-5D-5L/EQ-5D-Y)

LIST OF ABBREVIATIONS/GLOSSARY

Abbreviation	Explanation
AE	Adverse Event
ASIA	American Spinal Injury Association Impairment Scale
CI	Chief Investigator
CONSORT	Consolidated Standards of Reporting Trials
CRF	Case Report Form
C-spine	Cervical spine
CTU	Clinical Trials Unit
DMC	Data Monitoring Committee
EQ-5D-5L	EuroQol five-domain health utility measure (five level)
EQ-5D-Y	EuroQol five-domain health utility measure (Youth)
FIM	Functional Independence Measurement
GCP	Good Clinical Practice
ICF	Informed Consent Form
IRAS	Integrated Research Application System
ISRCTN	International Standard Randomised Controlled Trial Number
MRC	Medical Research Council
NIHR	The National Institute for Health Research
PI	Principal Investigator
PPI	Patient & Public Involvement
QoL	Quality of Life
RCT	Randomised Controlled Trial
REC	Research Ethics Committee
R&D	Research and Development
SAE	Serious Adverse Event
SchARR	School of Health and Related Research
SOP	Standard Operating Procedure
TARN	Trauma Audit & Research Network
TSC	Trial Steering Committee
VOI	Value of Information
WCTU	Warwick Clinical Trials Unit

1. BACKGROUND

1.1 Existing knowledge

NHS Ambulances use cervical collars for spinal immobilisation in large numbers of “at risk” injured patients (~ 80,000/year in UK, 5 million/ year in USA¹) but the numbers of patients shown to have a significant cervical vertebrae or spinal cord injury (SCI) is much less; 5476 in 2017 (from national major trauma registry, Trauma Audit & Research Network- TARN) with just under one third having cervical SCI (n=1376). A large number of patients are immobilised due to the challenges, even using the NICE decision rule, to confidently rule out unstable cervical spine (c-spine) fractures. Most civilian trauma is “blunt” (falls and road traffic collisions), where precise injury assessment is not possible in unconscious patients and difficult in conscious patients, who may have whiplash muscle injury, and may initially appear similar to a patient with an unstable spinal fracture. This means that at least 75% of patients exposed to the discomfort and complications of spinal immobilisation have no potential benefit. In the majority of immobilised patients, injuries to the spine are ruled out by assessment or imaging in the emergency department (ED) which allows removal of immobilisation within hours; however, ruling out an unstable spinal fracture may take much longer in comatose patients with brain injuries. Previous reports suggested that after imaging, 2-4% of major trauma patients have a significant c-spine injury. A published study using TARN data from 1998-2009 shows 2.3% of major trauma patients had a significant c-spine fracture or dislocation and 0.8% had a cervical SCI diagnosed prior to hospital discharge². The expansion of TARN to all trauma-receiving hospitals and better access to imaging has seen the average age of major trauma patients increase considerably in the intervening decade (current TARN median age = 59 years). The most recent analysis in 2017 suggests the true prevalence of significant potentially unstable c-spine injury and SCI within major trauma patients is therefore more than double (6% & 1.8% respectively). In the older population, cord contusion without fracture (e.g. central cord syndrome) is also more common. Recruitment will occur across the UK ensuring areas with a high disease burden make a substantive contribution.

1.2 Hypothesis

The primary hypothesis is that movement minimisation (intervention) is deemed non-inferior (i.e., no worse) compared to triple mobilisation (control) in patients with potential c-spine injury (pre-imaging) following blunt trauma, in relation to motor function at hospital discharge following randomisation.

1.3 Need for a trial

Spinal Immobilisation has been an essential standard of potential spinal injury care for 20 years³. However, gold standard “Triple Immobilisation” can be associated with neurological harm (for example if used in patients who unknowingly have ankylosing spondylitis)^{4,5}. The natural history following spinal cord injury (SCI) is that it often worsens as cord contusion progresses and this may mistakenly be attributed to lack of immobilisation. Hence the costs of not understanding SCI and immobilisation include not just the cost of collars (in UK ~ £500,000 year), but the cost of health complications and associated medico-legal costs, which can be considerable⁶. There is a significant body of opinion questioning the benefits of cervical immobilisation^{7,8}. Several ambulance services in Scandinavia and Australia have reduced the use of cervical collars, without an overt increase in complications. This is known as movement minimisation. Movement minimisation uses head blocks or rolled blankets to minimise movement in coronal plane, with the option to sit up (if desired and not contraindicated due to other reasons) on an ambulance stretcher. However, robust evidence is needed to know if movement minimisation is non-inferior than triple immobilisation before adopting

across the NHS given the substantial personal, healthcare and medico-legal consequences of SCI⁹. It is vital that a well-structured trial resolves this issue.

A survey of 614 health care professionals (373 Pre-Hospital Care, 154 Emergency Medicine, 34 Neurosurgery, 11 ITU, 11 Care of Elderly and 11 Anaesthetics) has demonstrated that 80% feel that current c-spine immobilisation guidelines are not appropriate. The majority (81.4%) were happy to randomise patients with potential spinal injury to either triple immobilisation or movement minimisation techniques with 64.4% thinking this should not be restricted to a specific conscious level. Respondents prioritised incidence of neurological deficit (58.6%) and a functional outcome measure (49.9%) as primary outcome measures. This proposal describes a definitive randomised trial to determine the clinical and cost effectiveness immobilisation regimes for spinal cord injury.

This clinician survey, patient & public views and the pragmatic requirements of undertaking a trial informed the decision to use a functional outcome measure as the primary end-point, supported by important clinical (neurological deterioration, mortality, morbidity, adverse events, resource use) secondary end-points and health economic analysis. The trial will efficiently utilise the TARN data to support measurement of clinical & cost effectiveness. The trial will provide the definitive answer to whether it is appropriate to use movement minimisation compared to triple immobilisation, in patients with potential c-spine injury.

1.4 Ethical considerations

The trial will be conducted in full conformance with the principles of the Declaration of Helsinki and to Good Clinical Practice (GCP) guidelines. It will also comply with all applicable UK legislation (e.g., Mental Capacity Act 2005 (England and Wales) and Mental Capacity Act (Northern Ireland) 2016) and Warwick Standard Operating Procedures (SOPs). This has been agreed with the Sponsor. All data will be stored securely and held in accordance with UK GDPR.

This is a trial conducted in patients experiencing sudden and unexpected trauma and therefore there are ethical considerations in recruiting patients in this setting. Due to the emergency and distressing nature of the injuries, most potential participants will not have capacity for fully informed consent. In addition, it would be dangerous and inappropriate to delay treatment to consult with a designated family member/consultee. As a result, emergency waiver of consent will be used in SIS. Consent will be obtained in line with the legal requirements for obtaining consent in patients without capacity in England and Wales (Mental Capacity Act 2005)¹⁰ and Northern Ireland (Mental Capacity Act (NI) 2016). Due to the need for deferred consent, prior to consent being obtained only non-identifiable data will be made available to the trial team.

1.5 CONSORT

The trial will be reported in line with the CONSORT (*Consolidated Standards of Reporting Trials*) statement¹¹.

Up-to-date information on CONSORT revisions, downloadable check lists and flow chart are available on the CONSORT web site: <http://www.consort-statement.org/>

2. TRIAL DESIGN

2.1 Trial summary and flow diagram

This is a UK-wide, open-label, pragmatic, phase 3, multi-centre, individually randomized, controlled, non-inferiority, clinical and cost-effectiveness trial, with blinded assessment of outcome during hospital stay and at 180 days. The trial design is described in PICO terms below and in Figure 1.

Population: Patients (all ages) in a pre-hospital setting with potential or suspected c-spine injury

[figure not shown]
Intervention: Movement minimisation

Comparator: Triple immobilisation (hard collar, blocks and tape/straps)

Outcomes: Clinical and cost effectiveness from randomisation, up to and including hospital discharge and at 6 months; longer term cost-effectiveness model

The main trial will be preceded by a 4-site pilot phase which will be accompanied by a value of information (VOI) analysis. This analysis will assess the feasibility and value for money of the proposed large-scale clinical trial.

Figure 1 Trial flow diagram

2.2 Aims and objectives

2.2.1 Primary objective

To determine whether movement minimisation is deemed non-inferior compared to triple immobilisation in relation to functional outcome (as assessed by the Functional Independence Measure Motor) at hospital discharge.

2.2.2 Secondary objective

Secondary objectives are to assess the effects of the immobilisation techniques on clinical, patient-centred and economic outcomes pre-hospital, in hospital (ICU and ward) and at 6 months (180 days) following randomisation.

Specifically, the effect of the two techniques used to immobilise patients will be assessed using the following outcomes:

- Pre-hospital analgesia;
- Functional Independence Measure Cognitive
- Neurological change (from the point of randomisation to hospital discharge);
- Mortality (at days 30, 90 and 180);
- Length of stay in critical care and hospital;
- Other interventions for c-spine injury;
- Quality of life, costs and resource utilization (6 months);
- Adverse events: pressure sores, aspiration pneumonia, intracranial hypertension

A further secondary objective is to conduct an internal pilot study to confirm the feasibility of the large-scale multi-centre trial.

2.3 Outcome measures

FIM: The primary outcome for the trial is the Functional Independence Measurement (motor) (FIM-motor). The FIM was developed as a functional assessment measure for all diagnoses in the rehabilitation setting and has been used to assess outcome in trauma populations away from the rehabilitation setting¹². The FIM consists of 18 items across 6 domains: self-care; sphincter control; mobility; locomotion; communication; and social cognition. There are 13 items related to motor activities and 5 assessing cognitive function. Each item rates the patient's level of disability on a scale from 1 to 7, with 1 representing total dependence and 7 describing complete independence without the need for an aid. Performance on each item is summed to form the FIM total score, which ranges from 18 (lowest function) to 126 (highest function). There are 2 additional sub-scores. The FIM cognitive score uses the 5 cognitive items to create a score from 5 (lowest cognitive function) to 35 (highest cognitive function). The FIM motor score sums the patient's performance on each of the motor items and ranges from 13 (lowest motor function) to 91 (highest motor function). The FIM motor score at discharge has also been found to be a significant independent predictor of return to work or study¹². Moreover, FIM motor reflects well the functional status of individuals following traumatic spinal cord injury¹³.

ASIA Impairment Scale¹⁴: The American Spinal Injury Association Impairment Scale (ASIA) is a standardized neurological examination used by the rehabilitation team to assess the sensory and

motor levels which were affected by the spinal cord injury. The scale has five classification levels, ranging from complete loss of neural function in the affected area to completely normal. Neurological deterioration is defined as the change from 'E' – normal to 'A-D' – impairment.

EQ-5D-5L¹⁵: The descriptive system comprises five dimensions: mobility, self-care, usual activities, pain/discomfort and anxiety/depression. Each dimension has 5 levels: no problems, slight problems, moderate problems, severe problems and extreme problems. The patient is asked to indicate his/her health state by ticking the box next to the most appropriate statement in each of the five dimensions.

The EQ-5D-Y¹⁵: (Used for youth patients). The descriptive system comprises the following five dimensions: mobility, looking after myself, doing usual activities, having pain or discomfort and feeling worried, sad or unhappy. Each dimension has 3 levels: no problems, some problems and a lot of problems. The younger patient is asked to indicate his/her health state by ticking the box next to the most appropriate statement in each of the five dimensions.

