2.3.1 Effectiveness

Primary effectiveness outcome:

- Total Functional Independence Measurement motor (FIM-motor) score at discharge. The FIM is an 18-item instrument measuring a person's level of disability in terms of burden of care. The FIM should be rated by the consensus opinion of a multidisciplinary team, but the evaluation is often performed by a single professional.

Secondary effectiveness outcomes:

- FIM-motor at 30 days, 180 days after randomisation at video clinic or follow up appointment;
- FIM-total and cognition scales at discharge, 30 days and 180-day at video clinic or follow up appointment;
- ASIA Impairment Scale at discharge;
- Mortality (at days 30, 90 and 180);
- Intervention for c-spine injury in the first 30 days or discharge (use of collar for > 2 weeks, halo brace, c-spine surgery);
- Discharge destination;
- Pre-hospital analgesic requirements (from Ambulance PRF).

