3.2.2 In hospital

The following data will be collected in hospital. These data will include:

- Duration of immobilisation in hospital
- Analgesia given (in hospital)
- CT scan appearance
- Details of cervical spine injury
- Mortality
- Evidence of infection
- The length of ICU stay and level of stay
- The length of hospital stay (dates)
- Interventions used for c-spine injury in the hospital and up to discharge
- Discharge destination
- Adverse events (e.g. chest infections, pressure sores, raised ICP)
- Other injuries sustained (randomisation to discharge)
- Injury Severity Score

The following will be collected as close as possible to the point of admission and discharge

- FIM (total and sub-scales)
- ASIA neurological scale
- Variables that will assist in the health economics analysis (including EQ-5D-5L/EQ-5D-Y).

If participants are discharged from the emergency department before a member of the local research team has had the opportunity to collect this data, their FIM-motor score will be recorded as 7 (total independence).

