4.3 Reporting Serious Adverse Events to the coordinating centre

The assessment and reporting of SAEs and related SAEs will follow the relevant Warwick CTU SOPs. Once a serious adverse event has been identified, information should be sent to the WCTU team at [contact], the WCTU QA team at [contact] and the Sponsor's Office at [contact] within 24 hours of the site becoming aware of the event. Reportable events should be recorded on the trial SAE form. The participant should continue to be followed-up until resolution of the event or a final outcome has been reached. Following reporting of a serious adverse event, any change of condition or other follow-up information should be reported by the same mechanism.

Events should be reported as a serious adverse event only if they:

- occur between randomisation and hospital discharge
- are serious (meet the criteria for Serious Adverse Events) AND are potentially related to trial participation, i.e. may have resulted from trial treatment;
- are not on the list of SAEs exempt from reporting (see section 4.3.1)

Examples of events that may be SAEs are;

- Use of one of the interventions causing a new injury that endangers the patient
- Unexpected cardiac arrest
- Sepsis related to use of collar
- Neuro-deficit

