4.3.1 SAEs exempt from reporting

Some events are anticipated as a result of the injury that has led to immobilisation of the spine, rather than the immobilisation itself. Many will be hospitalised with some requiring a stay in ICU/HDU. The following events will not need to be reported to WCTU because they are recorded in the CRF as an outcome or are anticipated as a result of the spinal injury rather than the intervention being studied:

- wound/skin breakdown
- pneumonia/chest infection
- evidence of intercranial hypertension
- other events directly attributable as a result of the participant's spinal injury

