5.1.2 In hospital through to discharge

For participants admitted to hospital a small amount of data will be collected on admission (FIM, ASIA neurological scale, analgesia given) by the local research team and at the point of hospital discharge. Data will be recorded using standardised case report forms (CRFs). Health-related quality of life will be collected using the EQ-5D-5L/EQ-5D-Y completed by the participant or, if they lack capacity, their consultee. The local research teams will be responsible for collecting this data.

At discharge FIM (completed by the appropriately trained clinical or research staff member), length of hospital stay, further treatment for spinal injury, discharge destination, and safety outcomes will be collected by the local research teams from the participant's medical records on the standardised trial CRFs. In addition, participants will also be asked to complete an EQ-5D-5L/EQ-5D-Y at discharge.

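### The defined neurological deterioration event omits worsening within ASIA grades A to D and, if the admission grade is its baseline, also misses impairment arising between randomisation and admission

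*Protocol*

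**What the plan says.** Protocol section 2.3 describes the ASIA Impairment Scale: "The scale has five classification levels, ranging from complete loss of neural function in the affected area to completely normal". It then fixes the event: "Neurological deterioration is defined as the change from 'E' – normal to 'A-D' – impairment".

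The secondary objective in section 2.2.2 is "Neurological change (from the point of randomisation to hospital discharge". The outcome listed in section 2.3.1 is "ASIA Impairment Scale at discharge", which is a grade and not a change.

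On timing, section 3.2.2 says of the ASIA and other scales: "The following will be collected as close as possible to the point of admission and discharge". Section 5.1.2, which here covers only those who become inpatients, says: "a small amount of data will be collected on admission (FIM, ASIA neurological scale, analgesia given) by the local research team". Table 1 ticks the ASIA for the hospital stay and for discharge, but not for baseline. Randomisation is on scene (section 2.8.1), and the trial summary starts the intervention at the first pre-hospital assessment.

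An unscaled neurological impairment item appears twice: in the randomisation app (section 3.2.1) and in the baseline data collected at hospital admission (the subsection numbered 7.2.2 within section 3.2). Neither is linked to the ASIA definition.

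On safety reporting, section 4.3 gives "Neuro-deficit" as an example of a possible serious adverse event (SAE). Section 4.3.1 exempts "other events directly attributable as a result of the participant's spinal injury".

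**The concern.** New or worsening neurological deficit is the harm one would most want to see if a less restrictive method were unsafe. In the clinician survey in section 1.3, neurological deficit was the most favoured primary outcome (58.6%, against 49.9% for a functional measure). The same section justifies a functional primary outcome partly because neurological deterioration supports it as a secondary one. The safety outcomes in section 2.3.2 include no neurological event, so this definition carries much of that weight.

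The definition is narrow in two ways. It ignores every step down the scale below E. And if the admission ASIA is the starting point, it ignores whatever happens between randomisation and that examination, which is the pre-hospital period when the randomised method is first applied.

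**Working it through.** **Which courses count.** The event is E at the starting assessment and A to D later. The protocol does not name the starting assessment, so both candidates are shown.

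| On scene | Admission ASIA | Discharge ASIA | Event if baseline is admission ASIA | Event if baseline is on-scene app item |
|---|---|---|---|---|
| Normal | E | D | Yes | Yes |
| Normal | C | C | No | Yes, if normal is read as E |
| Normal | D | A | No | Yes, if normal is read as E |
| Impaired | D | A | No | No |
| Impaired | B, having worsened before arrival | B | No | No |

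The fourth row is missed under any reading, because the definition has no rule for worsening within A to D. The second and third rows depend on the baseline. The fifth cannot be recovered from the planned data, because the on-scene item has no stated grades.

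**Match to the window.** Section 2.2.2 starts the window at randomisation; the ASIA starts at admission. With an admission baseline the event covers admission to discharge only.

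**Conditioning.** Under that baseline only participants graded E at admission can have an event. That grade is observed after randomisation and after the method has been applied. If the methods differ in impairment before arrival, the two groups at risk are no longer comparable by randomisation.

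**Scale.** No deterioration rate is given, nor the share graded A to D at admission, so missed events cannot be computed. Section 1.1 gives cervical cord injury in major trauma patients as 0.8% (1998-2009 registry data) and 1.8% (2017 analysis). Assuming these apply to the trial:
- 0.008 × 8316 = 66.5, about 67 participants (33 per arm)
- 0.018 × 8316 = 149.7, about 150 participants (75 per arm)

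These are participants with cord injury, not missed events. An unknown share would be A to D at the first ASIA.

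**How far FIM-motor helps.** The score runs from 13 to 91, a range of 78. If every cord-injured participant in one arm lost the whole range, the arm mean would move by 0.018 × 78 = 1.40 points. With 4158 × 0.85 = 3534 evaluable per arm, the half-width of the 95% interval is 1.96 × 25.93 × √(2/3534) = 1.21. An observed difference of −1.40 would give a lower bound of −2.61, beyond the margin of −2. If only one in ten of them (an illustrative assumption) lost the whole range, the shift would be 0.14 points and would be lost in the noise. So FIM-motor responds to extreme harm but not to harm in a small part of this group.

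**Primary sample size.** A margin of 2, SD 25.93, one-sided 2.5% and 90% power give 3533 per arm; 3533/0.85 = 4157 per arm, or 8314 in total, against 8316 stated. The plan's figure reproduces, and nothing here changes it.

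**The case against.** The strongest reply is that the protocol captures more than the defined event does.

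- The trial summary and section 3.2.2 allow immobilisation to continue in hospital. A change from E to A-D after the admission ASIA, while immobilisation continues, meets the definition. A reader might infer that no worsening during immobilisation is ever counted; the documents do not support that.
- The discharge ASIA grade is already a secondary outcome with no condition on the admission grade. Compared between randomised arms, it can show both kinds of worsening that the event misses. How it is modelled may properly be left to the SAP.
- Section 2.3 names no baseline, and the app records neurological impairment. If that item is the starting point, new impairment before arrival can count. So one cannot say that capture before admission is zero; one can say that the baseline is not fixed. The item has no scale, and its list also includes the time of arrival in hospital, so when it is completed is unclear.
- Section 4.3.1 is limited to events anticipated from the injury rather than the intervention, and the DMC also sees interim outcomes (section 7.10). The exemption is therefore not a blanket one. What remains is an unclear boundary, judged by sites that may know the allocation in an open-label trial.

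Two further inferences should be resisted. One is a figure for missed events: 1376/80,000 = 1.72%, and 1.72% of 8316 is 143, but this is again a count of assumed cord injuries, and it divides a registry count by an approximate number of immobilised patients. The other is that the neurological results are biased towards no difference. Losing events before admission could act in that direction for the defined event, but no size can be given, and the discharge ASIA comparison is free of the baseline problem.

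These points narrow the concern. None of them brings worsening within A to D into the defined event or settles which assessment is the baseline.

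**Conclusion.** The concern holds in a limited form. The omission of worsening within A to D follows directly from the definition and needs no assumption. The loss of new impairment before admission, the mismatch with the stated window and the conditioning on a post-randomisation state all hold if the admission ASIA is the baseline. That is the only early ASIA the protocol schedules, but the protocol does not say that it is the baseline.

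The number of events affected is unknown. The 67 to 150 participants with cord injury are for scale only and rest on major-trauma prevalences carrying over to everyone randomised.

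This is a secondary outcome, and the non-inferiority decision rests on FIM-motor. It should be fixed, but it does not undermine the primary analysis.

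**What to change.** 1. In section 2.3, define deterioration as new impairment, or a fall of one or more ASIA grades, between randomisation and discharge.
2. Name the baselines. For new impairment, use the neurological impairment item in the randomisation app, and state that it is recorded on scene. For worsening within A to D, use the admission ASIA.
3. Make the between-arm comparison of discharge ASIA grade in all randomised participants, without conditioning on admission grade, the main neurological analysis. Section 3.2.2 has a rule for FIM-motor in participants who leave the emergency department before assessment but none for the ASIA. The analysis will need one, and a rule for deaths before discharge.
4. Reconcile sections 4.3 and 4.3.1 so that new or worsening neurological deficit is not exempt from SAE reporting and reaches the DMC by arm.

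The cost is mainly wording, plus a few more SAE forms. The on-scene item is coarser than a full ASIA examination, so worsening within A to D before admission will still not be measurable as a change; the discharge comparison has to carry that part. An on-scene baseline that was not recorded at the time cannot be recovered later, so the second change should come early.
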